# 1) Study Title

Pulsewatch: Smartwatch Monitoring for Atrial Fibrillation After Stroke

## 2) IRB Review History\*

The application has never been submitted for review by an external IRB. NHLBI R01HL137734-01A1 from the NIH is funding this project.

## 4) **Objectives\***

The objectives of this project are to develop a mobile device application with providers and patients that is both usable and accurate. The mobile device application will collect and extract RR interval data and use real-time algorithms for accurate detection of atrial fibrillation (AF) from mobile devices, including a smartwatch. Our central hypothesis is that a wrist-based wearable paired with a smartphone application will detect paroxysmal AF (pAF) with high sensitivity and specificity when compared to conventional cardiac monitors and will be found acceptable by stroke and cardiology patients and their providers. To accomplish this goal, our study will have two phases, a developmental phase and a testing phase. The overall objective will be accomplished by testing our central hypothesis after achieving the following specific aims:

## Part I (Aim 1):

-To develop a robust and comprehensive mobile device application for analysis of heart rate interval series followed by real-time detection of paroxysmal AF and atrial flutter using our previously developed AF detection algorithm using smartwatch.

-To increase the accuracy and acceptability of our smartwatch-based pAF detection technology by involving older stroke patients and their providers in the design of the application.

## Part II (Aims 2-3):

-To evaluate the performance of a smartwatch for pAF detection in stroke patients and/or to monitor patient who are at stroke risk with  $CHA_2DS_2$ -VASc score  $\geq 3$  by examining over 14 days the accuracy of pAF detection from Pulsewatch vs. a state-of-the-art cardiac monitoring device.

-To evaluate rates of adherence and factors associated with successful longer-term smartwatch use among up to 60 randomly selected stroke patients and/or who have a  $CHA_2DS_2$ -VASc score  $\geq$ 3 enrolled in our 14-day validation study. These randomly selected participants will be asked to use the smartwatch/phone dyad for 30 days. We will explore the impact of smartwatch use over 30 days on patient-reported quality of life, anxiety, and self-efficacy compared up to 60 usual-care patients.

Learnings from these new objectives will support our future goal to extend monitoring periods to many months or years, surpassing the capabilities of event monitors.

## 5) Background\*

Atrial Fibrillation (AF) is the most common sustained dysrhythmia worldwide. Although new AF treatment strategies have emerged over the last decade, a major challenge facing clinicians and researchers is the paroxysmal, often short-lived, and frequently asymptomatic nature of AF. Given that paroxysmal and asymptomatic AF is a growing clinical and public health problem, better, less expensive, and more readily available AF detection technologies are needed. There

is, therefore, a pressing need to develop methods for readily-accessible monitoring devices powered by accurate AF detection algorithm in order to improve patient care and reduce healthcare costs associated with treating these arrhythmias and their complications.

Novel technologies for AF detection have important clinical and research applications for AF screening and monitoring. As was emphasized by a recent National Heart, Lung and Blood Institute (NHLBI) expert panel, there is a pressing need to develop methods for accurate AF detection and easily accessible monitoring devices. To this end, we have previously developed a sensitive, real-time realizable algorithm for accurate AF detection using commercially available, clinically applicable electrocardiographic recordings. Our AF algorithm has been tested using the MIT-BIH AF database and Holter recordings, shown to be accurate, and is now commercially available in a new Holter monitor from Scottcare Corporation. We have also made improvements to the algorithm so that it can detect AF episode that is as short as 12 beats. Further, we have recently developed a software application to measure heart interval series, which can be used to detect AF in real time from pulse plethysmographic (PPG) devices. Given the ever-growing popularity of smartphones and smartwatches, our approach to AF detection using a mobile device will give patients as well as healthcare providers the opportunity to monitor these arrhythmias under a wide variety of conditions outside of the physician's office and outside of the patient's home.

Because our approach uses only standard smart device hardware (e.g., iPhone or Samsung watch), it is cost-effective, thereby leading to better acceptance and use by patients. Our mobile health for AF detection platform has the potential to markedly change the traditional delivery of healthcare, allowing for more frequent, rapid, and patient-directed AF detection. We will test the acceptability and accuracy of our smartwatch-app dyad using smart devices (a smartphone and smartwatch) to be collected from recruited stroke or transient ischemic attack survivors at risk for AF or patients with a CHA2DS2-VASc score of  $\geq$  3 at risk for a stroke or transient ischemic attack. We believe this research will result in rapid translation into innovative AF detection solutions, leading to more effective monitoring and diagnosis of these common arrhythmias. Finally, the proposed work has the potential to significantly reduce healthcare costs and enhance patient care by accurately and rapidly establishing the diagnosis of AF in at-risk groups, thereby providing clinicians with an opportunity to prevent secondary complications of these life-threatening arrhythmias.

Stroke survivors and individuals at high risk for incident stroke require cardiac monitoring for AF, the single greatest risk factor for stroke: Current American Stroke Association stroke management guidelines recommend: "For patients who have experienced an acute ischemic stroke or TIA with no other apparent cause, prolonged rhythm monitoring (≈7-14 days) for AF is reasonable" and recommended. In addition, patients with AF risk factors, including hypertension, diabetes mellitus, vascular disease, and prior episodes of AF or atrial flutter should be monitored for recurrence. This is because AF is the primary cause of ~15% of all strokes and AF recurrence and burden relate to stroke. Moreover, patients with AF, if not treated with anticoagulation therapies, tend to have larger strokes that lead to significant disability. One in 4 patients leaves the hospital without a cause of their stroke identified (cryptogenic strokes). Of the 200,000 American patients diagnosed with cryptogenic stroke yearly, 1 in 5 has paroxysmal AF identified if long-term post-discharge cardiac monitoring is used. Unfortunately, traditional in–hospital monitoring following stroke identifies AF in only ≈5% of cases and longer-term monitoring, although effective, is rarely used as it presently necessitates the implantation of an expensive invasive device (e.g., Medtronic LinQ monitor or pacemaker).

Most existing smartphone apps can detect heart rate, but they cannot detect cardiac rhythm. AF detection algorithms used in cardiac devices and monitors are rudimentary and require the use of electrodes or invasive devices implanted underneath a patient's skin. AliveCor - a smartphone-based arrhythmia detection platform - pairs ECG electrodes with a smartphone running a proprietary app, enabling single-lead ECG and intermittent pAF monitoring. No existing algorithm for AF detection uses the combination of passive monitoring, pattern recognition, computational speed, and robust noise cancellation routines our solution employs. Additionally, although there are several smartwatches and wearables, including those from Apple, Philips, and Fitbit, that are capable of heart rate monitoring, the Samsung platform offers 3 unique advantages: 1) provides researchers with access to a secure data management system designed for research (Artikcloud), 2) allows for independent development of open-source applications, 3) has a smartwatch capable of out-of-the-box pulse monitoring.

In our new "Pulsewatch study," we propose to hone our existing smartphone app to work with a smartwatch in concert and in a manner that is accessible and usable by elders with, or at risk for, stroke with input from expert providers and patients. The app will use prompts to promote adherence to daily use of the smartwatch during the monitoring period and will prompt participants to perform a pulse check if they experience a symptom of AF.

## 6. Inclusion/Exclusion Criteria

## Part I: Design/Development of the app-smartwatch dyad

### Patient (and Caregiver) Focus Groups and Hack-a-thon (Part 1):

**Inclusion:** For patients: history of TIA or stroke, presenting at the UMass Memorial Medical Center (UMMMC) inpatient service or ambulatory clinic (neurology clinics and cardiovascular clinics included), age  $\geq$  50 years. For patient caregivers: history of caring for a family member or loved one with the inclusion criteria listed above in the last five years. For both patients and patient caregivers: able to sign informed consent, and willing to participate in a focus group and/or Hack-a-thon.

**Exclusion**: For both patients and patient caregivers: serious physical illness (e.g., unable to interact with a smart device, or communicate verbally or via written text) that would interfere with study participation, lacking capacity to sign informed consent, unable to read and write in English, plans to move from the area during the study period, unwilling to complete all study procedures, including attending a focus group and/or Hack-a-thon.

### **Provider Focus Groups and Hack-a-thon for Part 1:**

**Inclusion**: medical provider (i.e., cardiology fellow or neurology resident, attending cardiologist, attending neurologist, stroke or cardiology nurse practitioner) at UMMMC, >3 years of experience providing care to stroke or TIA patients, willingness to complete informed consent, and willingness to participate in a focus group and/or Hack-a-thon.

### Part II: Study of the app-smartwatch dyad

**Inclusion:** History of TIA or stroke, presenting to the inpatient UMMMC neurology service or ambulatory clinic (neurology clinic or cardiovascular medicine clinic/monitoring station), and/or has a  $CHA_2DS_2$ -VASc score  $\geq$ 3, age  $\geq$  50 years, capable of signing an informed consent, willing

Pulsewatch ISP V 1.5 Docket#: H00016067

## PULSEWATCH INVESTIGATOR STUDY PLAN

and capable of using Pulsewatch (smartwatch and smartphone app) daily for up to 44 days and returning to UMMMC for up to two study visits.

A CHA2DS2-VASc score is a widely used and validated instrument recommended for use by cardiologists to determine stroke risk in atrial fibrillation patients. CHA2DS2-VASc score relates to stroke risk among individuals with AF and those free from a known diagnosis of AF. Using a CHA2DS2-VASc score as an inclusion criterion during screening for possible subjects will enable the study to approach patients at high risk for stroke who could benefit from continuous monitoring.

**Exclusion:** Major contraindication to anticoagulation treatment (i.e., major hemorrhagic stroke). Plans to move out of the area over the 44-day follow-up period. Unable to read or speak English. Unable to sign consent. Unable or unwilling to return for potential study visits (up to two over a 44-day study period). Patients with known allergies or hypersensitivities to medical grade hydrocolloid adhesives or hydrogel. Patients with life threating arrythmias who require in patient monitoring for immediate analysis. Patient with implantable pacemaker as paced beats interfere with the ECG reading.

Major contraindication to anticoagulation treatment is an exclusion due to the goal of this study, which is to help prevent secondary stroke; anticoagulation is a mainstay treatment for these patients. Therefore, if patients are unable to receive anticoagulation treatment, they are not in the ideal target population for this study.

**Special Populations:** 

- Adults unable to consent Will not be recruited for this study.
- Individuals who are not yet adults Will not be recruited for this study.
- Pregnant women Will not be recruited for this study.
- Prisoners Will not be recruited for this study

If we struggle to enroll a sufficient number of participants using the campus and clinics outlined above, we will recruit at the stroke treatment centers or cardiology clinics at UMass Memorial - Health Alliance Hospital in Leominster, MA, and at UMass Memorial - Marlborough Hospital in Marlborough, MA. The inclusion/exclusion criteria will otherwise remain the same.

## 7. Study-Wide Number of Subjects\*

Not a multi-site study.

## 8. Study-Wide Recruitment Methods\*

Not a multi-site study

## 9. Study Timelines\*

The first year to 1.5 years of the study will be focused on achieving Aim I (**Part I – design of the application**). Focus groups will be scheduled on a rolling basis over Year 1 and will be strongly influenced by the coordinator and room availability, as well as participant preference. The Hack-

a-thon will also be scheduled at or around the end of Year 1 of the study (Spring 2019). Participants will be advised of when the event will be held.

Enrollment for Aims 2-3 (**Part II**) will begin in Year 2 and will run for 3 years. At enrollment, participants will be asked to use a cardiac monitor for 14 days and return for a study visit to evaluate device usability and accuracy. Thereafter, we will ask a randomly selected subsample to continue to use the device for an additional 30 days for a total of 44 days. We will hold additional semi-structured exit interviews for select Aim 2 intervention participants who used the Pulsewatch devices for 14 days.

Study Year	1				2				3				4			
Quarter	1	2	3	4	1	2	3	4	1	2	3	4	1	2	3	4
DEVELOPMENT/ENHANCEM	ИE	N٦	(/	۱in	n 1	)										
Formative patient focus groups & provider interviews																
Analysis of formative qualitative data																
"Hack-a-thon" Stakeholder- Agile Team Meeting																
Refine & Integrate AF, skin contact, & MNA algorithms																
EVALUATION/DEPLOYMENT (Aims 2 and 3)																
Smartwatch deployed in stroke population																
Follow-up interviews/exit interview assessment of app																
Data analysis																

The Pulsewatch study will be conducted over a 4-year period; see table below.

## 10. Study Endpoints\*

Not only will we achieve our central hypothesis with our aims, but we will be able to complete the following endpoints as well:

### Part I:

- Using focus groups, we will gain feedback on the:
  - App prototype and system as a whole
  - Role of caregivers in technology use
  - Barriers and facilitators of use
  - Preferences and usability of features
  - o Enhancements to text and ambient messaging
  - Communication system design
  - Provider preferences regarding notification criteria and format
  - Potential implementation settings
  - o Information display, graphical images, and message content
- Hack-a-thon endpoints will ensure developers:
  - Hear patient and provider needs
  - Obtain feedback on information display, graphical images, and message content

### Part II:

- Quantitative Endpoints: We will evaluate the performance of the application for detection of atrial fibrillation compared to a gold-standard ECG monitor. We will also evaluate adherence to the system and factors associated with adherence.
- Qualitative Interview Endpoint: Impact of app use on quality of life, anxiety, and selfactivation (using our questionnaire at baseline, at the 14-day follow-up, and the 44-day follow-up). This information will be obtained from study questionnaires administered at enrollment, at the end of Aim 2 at 14 days post-enrollment, and after study completion 44 days post-enrollment, as well as from exit interviews convened with up to 30 selected participants after they use the system.

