All participants will be given a Device Handout regarding instruction for the appropriate devices they are given. In addition, the study team will review with each participant all instructions regarding how the Cardiac Insight patch functions and the participant's responsibility. The participant will also go home with information regarding the patches (see in eIRB, Cardea Solo Quick start guide- this will be added the Device handout). The study team, specifically the PI, may need to contact participants directly about their results. This will be disclosed in the informed consent form that participants sign.

The Aim 2 intervention participants (up to n=90) will be asked to use the same gold-standard Cardiac Insight patch monitor device for 14 days as the control group described above. Aim 2 intervention participants will also be given a Samsung smartwatch and a Galaxy smartphone. The Samsung smartwatch and Galaxy smartphone are standard devices that are sold commercially and will be labeled, nonetheless, as research devices. If the participant has a smartphone that is compatible to our Pulsewatch app, then we will download the app onto the participant's smartphone.

The Aim 2 intervention group (up to n=90) will be asked to self-monitor using the Pulsewatch system for at least 9 hours daily for 14 days. The intervention system is designed to be minimally intrusive. Participants will be asked to return all study devices (2 Cardiac Insight patches, Samsung smartwatch, and Galaxy smartphone) at the end of their 14 days of use at the follow-up study visit. Participants will be asked to complete a questionnaire at this follow-up study visit and will be compensated.

At enrollment in Part II, all study participants will be informed of the possibility that they may be randomly selected at the completion of their 14-day monitoring period to use the Pulsewatch system for up to 30 days. We chose to assign a larger proportion of participants to the Aim 2 intervention group because the primary analyses for Aims 2 and 3 are focused on Pulsewatch users.

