**Diagram 1b. Participant process of Part II, trial phase. This diagram outlines what the participant process is after 14 days and after 44 days. Group names are corresponding to the Part II Consent V1.2 form submitted in eIRB.** Please note: for this "Randomization\*" we would like to ask permission from the IRB for an adaptive plan; refer to section 13 Data Analysis and Management, sub section AF Detection Analysis for this plan. We have provided further details about this process below.

To accomplish Aim 2, we will examine the performance of Pulsewatch monitoring compared to conventional cardiac monitoring for pAF detection (accuracy of detection). We will also explore the participant factors (e.g., hearing or cognitive impairment) associated with app performance.

By enrolling patients from both inpatient and outpatient clinical settings, we will be able to recruit patients who have stroke/TIA and/or who are at risk for stroke (deemed to have a

CHA2DS2-VASc score  $\geq$ 3). At the end at 14 days, if less than 5% of participants have AF based on the gold-standard Cardiac Insight patch, then we would like to ask participants to extend the use of their monitors for further monitoring. (See Section 13, Data Analysis and Management, AF Detection Analysis.)

To accomplish Aim 3, we will randomly select 60 participants from both the intervention group and the control group of Aim 2 at the end of the 14 days and ask them to continue using, or begin using, the Pulsewatch system to upload their pulse recordings. We will also provide participants randomized to the Aim 3 intervention group with a gold standard AliveCor Kardia mobile ECG device to use if they wish to verify their pulse reading from the smartwatch. We will also examine factors (e.g., vision) participants report related to their adherence to using the Pulsewatch system. The 60 participants randomly selected to the Aim 3 control group will not use any devices during this time.

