Research staff (RA or study coordinator) will provide enrolled participants with detailed instructions about the operations and proper usage of the Pulsewatch smartwatch, smartphone

apps (including the Pulsewatch app and AliveCor app), ECG, and 14-day monitor. A checklist and a YouTube video may be made available to participants to remind them of how to charge. wear, and perform ECG self-checks using the smartwatch and phone app. Participants (including all control and intervention participants) will return smartphones and watches and/or 14-day monitors after their study visit at 14 days. For Aim 2 intervention participants, pulse and ECG data from the smartwatch and annotations/adherence data from smartphones will be uploaded by study staff after the 14-day visit to the secure cloud server. Aim 2 control participants will be provided instructions on the gold-standard Cardiac Insight patches. Study staff will be available via telephone to answer any questions participants have with using the smartwatch and smartphone, charging the battery, and uploading data throughout the 14-day trial period as needed. The 60 randomly selected participants, who were consented at baseline to participate in this aim will receive additional training at their 14-day study visit, taught on how to use the AliveCor Kardia mobile device and will use the Pulsewatch smartwatch and smartphone for an additional 30 days. Participants in Aim 3's intervention group will be asked to upload pulse and ECG data from AliveCor if they would like to do a self-check after receiving the watch notification. The secure server architecture used by Samsung minimizes the potential for loss of health information and is similar to one used in our prior work.

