# **Usability Analysis:**

We also aim to examine whether participant characteristics (e.g., demographics, level of technology use, cognitive impairment, etc.) affect usability and adherence of the Pulsewatch system. Usability will be examined by semi-structured interviews, investigator generated

questions regarding user experience, and the System Usability Scale (SUS), a validated instrument for perceived system usability. Investigator generated questions will have responses in a 5-point Likert-like scale, and ordinal regression will be used to evaluate participant characteristics that may be associated with more favorable responses regarding usability of the Pulsewatch system. The SUS score ranges between 10 and 100, and linear regression will be used to examine the participant level factors that are associated with higher SUS scores. Logistic regression will also be used to examine whether certain participant factors are associated with having a SUS score of over 68, the acceptable cut off being deemed as a highly usable system.

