## Adherence Analysis:

In Aim 3 of Part II of the study, adherence will be operationalized to determine whether pulse recordings were present on each day over the 30-day period. We will examine whether participant characteristics, e.g., sex, cognitive impairment, or stroke-related quality of life, affect the likelihood of adherence over the 1-month study period. We will use a mixed effects logistic regression model, including the participant as the random effect to capture the correlation among repeated measures from the same participant, using participant characteristics as the fixed effects, and a binary indicator of daily adherence as the dependent variable. We will also examine the adherence time-trend by including time (day) as a fixed effect in the model and participant as a random effect to estimate the slope of adherence over time. To examine whether the time trend varies by participant characteristics, we will include the interaction between characteristics and time in the model so that the slope of adherence over time can be estimated for each category of participant characteristic variables and be compared among the categories (e.g., pAF diagnosed vs. no pAF). Secondary analyses will examine rates of adherence to Pulsewatch ECG prompts and will compare Pulsewatch users to the usual care group with respect to stroke-related quality of life, anxiety, and self-activation. We will calculate the change score between baseline and 1 month as a dependent variable. First, a t-test will be used to compare 2 study groups on the change score. We will use a linear regression model, which will include group indicator (Pulsewatch users vs. usual care) as the independent variable and possible confounders (e.g., medication adherence and participant demographics) as covariates, to estimate adjusted group differences on the change scores.

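### The 14 days of adherence data on up to 90 Aim 2 users enter no adherence analysis, and the Aim 3 day trend ignores prior watch use

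*Protocol*

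**What the plan says.** Three places in the protocol state the adherence objective, with different scope.

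- Section 4 (Part II, Aims 2-3) is narrow: "To evaluate rates of adherence and factors associated with successful longer-term smartwatch use among up to 60 randomly selected stroke patients", followed for 30 days.
- Section 10 (Part II) is general: "We will also evaluate adherence to the system and factors associated with adherence".
- Section 13 (Usability Analysis) is also general. It will examine whether participant characteristics "affect usability and adherence of the Pulsewatch system", but the models it then gives are for usability only.

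One adherence outcome is defined, in Section 13 (Adherence Analysis): "In Aim 3 of Part II of the study, adherence will be operationalized to determine whether pulse recordings were present on each day" of the 30-day period. A mixed effects logistic model with a participant random effect is fitted to it, with day as a fixed effect for the time trend. The SAP (Aim 3 Analysis, Aim 3 Power) has the same model, for 30 users rather than 60.

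Adherence data also exist for Aim 2. Up to 90 intervention participants "will be asked to self-monitor using the Pulsewatch system for at least 9 hours daily for 14 days" (Section 11, Part II), and their "annotations/adherence data from smartphones will be uploaded by study staff after the 14-day visit to the secure cloud server" (Section 11, Deployment of devices/app). No outcome or model for these data is given. For Aim 3, the protocol will "randomly select 60 participants from both the intervention group and the control group of Aim 2 at the end of the 14 days", so the Aim 3 users include both people who have worn the watch and people who have not.

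**The concern.** A stated Part II objective has no analysis for a large part of the data that bear on it. Early use by the Aim 2 users who are not selected for Aim 3 (about 45 people) is never modelled. Whether participant characteristics go with use is the primary Aim 3 question, and the between-person comparison rests on few people, so unused person-time is worth a deliberate decision.

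The time trend has a second problem. Aim 3 day 1 is the first day with the watch for a former control, but the fifteenth for a former Aim 2 user. If use declines with time since issue, one slope over Aim 3 days averages two different stretches of that decline. A characteristic that happens to be unbalanced between the two kinds of user could then pick up part of the difference.

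**Working it through.** **Inputs.** Up to 90 Aim 2 users for 14 days; 60 Aim 3 users (protocol) or 30 (SAP) for 30 days; 120 participants in all, 90 intervention and 30 control; correlation .2 to .5, 12 vs 18 users, 80% power and 5% type I error (SAP, Aim 3 Power; two-sided assumed). Assumption: simple random selection of 60 from 120.

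**The plan's own figure.** The SAP gives detectable differences of 12%-16% from a base of 50%, and 9%-12% from a base of 80%. I used a two-proportion normal approximation with effective size n × 30/V. Under AR(1) correlation r, V = 1 + 2Σ(1 − k/30)r^k, which is 1.479 at r = .2 and 2.867 at r = .5. The results are 11.5%-15.8% and 8.6%-11.5%, so the SAP figures reproduce. Exchangeable correlation, V = 1 + 29r, gives 23.7%-33.9% at base 50% and does not reproduce them. The planned participant random effect implies the exchangeable form, so both structures are carried below.

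**Watch-days left out.**
- 60 Aim 3 users: 90 × 14 = 1,260 and 60 × 30 = 1,800, so 1,260/3,060 = 41.2%.
- 30 Aim 3 users: 1,260/(900 + 1,260) = 58.3%.

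**Expected overlap.** Prior users among the 60: 60 × 90/120 = 45. Former controls: 60 × 30/120 = 15. All watch-days together are then 45 users with 44 days, 45 with 14 and 15 with 30: 105 distinct users.

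**Information on a between-person factor.** I = Σ m/V(m) over users, where m is days observed. Example, exchangeable, r = .2: V = 9.6, 3.6 and 6.8 for 44, 14 and 30 days. Aim 3 alone: 1,800/6.8 = 264.7. All days: 1,980/9.6 + 630/3.6 + 450/6.8 = 206.3 + 175.0 + 66.2 = 447.4. Share left out: 1 − 264.7/447.4 = 40.8%.

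| Structure, r | Aim 3 only | All days | Left out | SE ratio (all/Aim 3) |
|---|---|---|---|---|
| AR(1), .2 | 1,216.9 | 2,069.7 | 41.2% | .767 |
| AR(1), .5 | 627.9 | 1,069.7 | 41.3% | .766 |
| Exchangeable, .2 | 264.7 | 447.4 | 40.8% | .769 |
| Exchangeable, .5 | 116.1 | 201.0 | 42.2% | .760 |

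The SE ratio is the square root of the information ratio, so the standard error falls by 23-24% under either structure. On the SAP's power basis (AR(1), 40:60 split, base 50%), the detectable difference goes from 8.2-11.3 points with 60 users to 6.3-8.7 points with all days.

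**Sensitivity.** At most 30 of the 60 can be former controls, so prior users number 30 to 60. Over that range the share left out is 41%-42% under AR(1) and 32%-49% under exchangeable correlation. With 30 Aim 3 users and proportional overlap it is 58.5%-59.1% under AR(1) and 66.8%-68.5% under exchangeable correlation.

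**The case against.** The strongest reply is that the restriction is deliberate. Section 4 asks about longer-term use in the randomly selected users, and the SAP makes one-month use the primary Aim 3 analysis. Days 1-14 are lost information only if early and later use are the same question. Conditions differ too: Aim 2 has the patch and staff upload, whereas Aim 3 has the AliveCor device, no patch and participant-prompted upload (Sections 11 and 12). A period main effect shifts the average level but does not let a characteristic act differently in the two periods. All of this stands, and it is why the Aim 3 model should stay primary. It does not supply an analysis for the wider objective in Sections 10 and 13, and it does not address the mixed starting points in the day trend.

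Two stronger readings are tempting, and the documents do not support them.

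- A reader might infer that the 90 Aim 2 users carry more information than the 60 Aim 3 users because people count for more than days. Under exchangeable correlation Aim 2 alone holds 1.32-1.45 times the Aim 3 information (350/264.7 and 168/116.1). Under AR(1), which reproduces the SAP's power figures, it holds only 0.71-0.74 times. The claim depends on the structure assumed.
- A reader might infer that everyone who stops using the watch before day 14 is excluded. Selection is random at day 14. The COVID-19 procedure conditions it on completing the questionnaire, which Section 11 allows by phone, and not on continued wear. A person who has stopped wearing the watch can still enter Aim 3. Only those lost before day 14 are absent. They may be replaced (Section 25), and no rate is given, so their number cannot be sized. Some of their Aim 2 data may also be missing, since pulse data are retrieved when the watch comes back. The SAP does plan interviews with users who stopped.

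**Conclusion.** The point holds as a gap between objective and analysis; no planned analysis is shown to be invalid. Adherence data from up to 90 Aim 2 users enter no adherence model, although Sections 10 and 13 state the objective without an Aim 3 limit.

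The size is 41% of planned watch-days at the protocol's 60 Aim 3 users, and about 41%-42% of the information under either correlation structure. That rests on about 45 prior users among the 60, full 14- and 30-day follow-up without the optional Aim 2 extension, and factor effects that are the same in both periods. If those effects differ, the figure does not measure information about longer-term use. At the SAP's 30 users the share is 58% of watch-days and up to 69% of the information.

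The missing term for prior watch use stands under the protocol's selection from both Aim 2 groups, whether or not the Aim 2 days are analysed.

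**What to change.** 1. Keep the 30-day Aim 3 model as the primary estimate for longer-term use. Add a term for prior watch use (Aim 2 arm), or make days since watch issue the time variable.
2. Define daily adherence for Aim 2 by the same yes/no rule, a pulse recording present that day.
3. Add a supplementary mixed logistic model on all Aim 2 and Aim 3 watch-days (about 105 users), with a study-period term and a factor-by-period interaction. Report the 14-day Aim 2 estimates separately. If the sponsor prefers not to analyse the Aim 2 data, the SAP should say so and why.
4. Reconcile 30 and 60 Aim 3 users between SAP and protocol, and restate the power accordingly.
5. Report how many users are lost before day 14.

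The cost is SAP wording and a little programming, with no new data and no added burden on participants. The pooled estimate answers the Aim 3 question only if factor effects are similar in the two periods. The interaction is there to examine that, and the pooled result should not replace the Aim 3 estimate.
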